Protocol version	V 1 Dated 16.5.2022
Objectives	
Primary objective	Pilot study to assess the feasibility of a large multicentre randomised trial of perioperative fluvoxamine in the prevention of postoperative delirium
Secondary objectives	
1) Obtain the trial enrolment rate per month2) Reasons for screening failure/enrolment refusal into the trial3) Assess the influence of perioperative fluvoxamine on the rate and severity of delirium on POD1–44) Assess the rate and severity of adverse effects of fluvoxamine5) Examine the number of missed study drug doses due to adverse effects6) Assess the ability to acquire EEG recordings on POD1+27) Differences in EEG slow wave activity (0.5–6Hz) on POD1+2 with perioperative fluvoxamine8) Assess the ability to acquire plasma biomarkers IL-8 and NfL on POD1+29) Group differences in levels of plasma IL-8 and NfL on POD1+210) Assess the fraction of completed 3D-CAM assessments11) Influence of perioperative fluvoxamine on Delirium Rating Scale -Revised 98, 3D-Confusion Assessment Method-S, Richmond Agitation and Sedation Score on POD1–412) Influence of perioperative fluvoxamine on postoperative pain scores13) Influence of fluvoxamine on postoperative change in cognition, disability or depression scores.14) Differences in C-Reactive Protein (CRP), White Cell count (WCC) and troponin.
Study design	Double blind placebo-controlled randomized controlled feasibility trial
Planned sample size	46
Selection criteria	Elective non-cardiac, non-intracranial surgical patients who are older than 60 years old with an expected length of hospital stay of >2 days

Study procedure	Patients will be randomised to: (1) 100 mg fluvoxamine the night before surgery, AM and PM on the day of surgery, and AM and PM on POD1, or (2) placebo control
Statistical considerations	This pilot study is powered for a 25% recruitment rate in approached patients with a 95% confidence interval of 13%.
Duration of the Study	1 year

1. BACKGROUND AND INTRODUCTION

1.1. DISEASE/PROPOSED INTERVENTION BACKGROUND

Delirium is a disturbance in attention, cognition, and consciousness, an acute physiological consequence of medical events, such as hospital admission, surgery, sepsis, and pharmacological intervention.¹ It is characterised by a sudden onset and fluctuating course not otherwise explained by a pre-existing neurological disorder or medical condition.^{2,3} Common in older adults, it affects up to 50% of those in hospital with a healthcare burden estimated at \$152 billion per annum in the USA.⁴ Perioperative delirium has been associated with increased mortality,⁵ comorbidity,^{6,7} functional and neurocognitive decline,^{8,9} hospital readmission,¹⁰ and institutionalisation.¹¹ A recent meta-analysis (k=71) found older inpatients with delirium experienced a mortality risk three times that of those without delirium.⁵

The pathogenesis of postoperative delirium involves systemic inflammation^{12,13} where inflammation drives changes in synaptic activity, revealed as electroencephalogram slowing¹⁴, and consequent cognitive impairment. There is a proportional relationship between delirium severity and postoperative inflammation (notably IL-8)^{12,13}, suggesting a causal relationship. Inflammation also correlates with neuronal (neurofilament light and total tau)^{13,15,16} and myocardial injury (troponin)¹⁵ suggesting that blocking inflammation may protect against perioperative organ injury. Strategies to mitigate this rise in inflammation are urgently required.

Our animal and translational studies suggest that systemic inflammation drives a central inflammatory response, likely involving breakdown of the blood–brain barrier, and subsequent prostaglandin-mediated EEG slowing.

1.2. RATIONALE FOR PERFORMING THE STUDY

One strategy to suppress inflammation is through agonism of sigma-1 receptors which leads to suppression of pro-inflammatory cytokine release. Through modulation of the endoplasmic reticulum stress response via inositol response element-1 (IRE-1), sigma receptor agonism suppresses the transcription of proinflammatory cytokines,

suppressing the immune response. Many drugs target sigma-1 receptors, but the selective serotonin reuptake inhibitor, fluvoxamine, is a safe and potent agonist. Recent animal data shows that the powerful anti-inflammatory actions of fluvoxamine improve survival in sepsis animal models (20mg/kg intraperitoneal)¹⁸, including reductions in inflammatory cytokine mediators. *In vitro* assays shows that fluvoxamine reduces the upregulation of cyclooxygenase-2 that drives inflammation-associated prostaglandin synthesis¹⁹. It also suppresses cytokine release from human blood¹⁸. It exerts direct anti-neuroinflammatory actions in a parkinsonian disease model²⁰, a multiple sclerosis model²¹ and neuroprotection in a stroke model (20mg/kg)²². We have previously demonstrated in humans that fluvoxamine reduced clinical deterioration from COVID-19 in two RCTs,^{23,24} likely though its anti-inflammatory effects. Fluvoxamine has also been used to treat delirium in a series of case reports based on older adults and/or intensive care unit patients, underscoring its potential utility in the setting of delirium²⁵.

Fluvoxamine pharmacokinetics

Fluvoxamine pharmacokinetics (PK) are relatively stable with age and with deteriorating renal function, though caution is warranted in patients with hepatic failure. The serum half-life is approximately 21 hours. Due to the lipid soluble nature of the drug, the drug becomes concentrated in the brain²⁶ with a brain half-life twice that for plasma. These pharmacokinetic properties are ideal for an anti-inflammatory agent that may target the brain, reducing the central inflammatory response. Notably, postoperative neurocognitive decline is associated with both infiltration of circulating monocytes (consistent with a key role of IL-8 in delirium) and activation of microglia.²⁷ Furthermore, fluvoxamine’s slow redistribution from the brain may be ideal for reducing neuroinflammation and delirium severity even after discontinuation. Overall, these data suggest a concrete pathophysiologic pathway that could be pharmacologically attenuated through anti-inflammatory effects of fluvoxamine (**Figure 1**).

Currently, there are no established prophylactic perioperative medications that mitigate delirium risk. Furthermore, the role of inflammation in precipitating delirium has not been fully elucidated. The anti-neuroinflammatory effects of fluvoxamine have the potential to address both needs. Just as recent data suggest that fluvoxamine could be repurposed as a low-cost well-tolerated intervention for COVID-19,²⁸ perioperative administration has the potential to target a reduction of inflammation and injury within the brain.

Previous randomized controlled trials of prophylactic interventions to treat delirium have shown modest effectiveness. A reduction of systemic inflammation through the administration of corticosteroids²⁹ has not led to reductions in delirium, despite the extensive observational evidence to support neuroinflammatory hypotheses of delirium. Systemic corticosteroids may precipitate delirium and confer unwanted side effects on surgical wound healing, overall immunity, and hemostasis. Alternative prophylactic approaches have targeted sleep structure (e.g., dexmedetomidine) or symptoms (e.g., haloperidol).

Here, we target a putative pathway of delirium pathogenesis that may be both necessary in the perioperative setting and sufficient outside of the surgical arena.

[figure not shown]

Figure 1. **Schema of the putative neuroinflammatory pathway targeted by this proposal.**

FLU = fluvoxamine

Thus, this potential therapeutic approach has potential generalizability to different clinical settings.

The 3 aims we will address in this study are: **Aim (1)** Evaluate the feasibility of recruiting participants; **Aim (2)** evaluate the feasibility of administering perioperative fluvoxamine in a placebo-controlled trial; and **Aim (3)** evaluate the feasibility of collecting participant outcomes. Completion of this feasibility trial will provide strong preliminary data and an established multisite transdisciplinary team towards a competitive grant application. This future grant proposal would encompass a transcontinental RCT to evaluate the effectiveness of perioperative fluvoxamine at reducing postoperative delirium incidence and severity. Data from this feasibility study would serve as key preliminary data. Synthesizing enrollment rates (**Aim 1**), rates of protocol adherence for study drug administration (**Aim 2**), rates of tolerance of AEs (**Aim 2**), rates of collection of outcome measures (**Aim 3**), estimates of EEG SWA/NfL/IL-8 variance (**Aim 3**), and a minimal clinically significant effect of fluvoxamine at reducing delirium severity of 20%, we will calculate the anticipated numbers of eligible and approached patients needed for this future trial. Based on existing data, the RCT would likely target enrollment of 280 patients, based on a minimal clinically important effect size of a 20% reduction in delirium severity. This innovative investigation would include mechanistic sub-studies to further enhance our understanding of delirium pathogenesis and longer-term implications on cognition and quality of life. The sub-studies will focus on how inflammation disrupts normal brain electrophysiological activity, alters circadian biology, and induces neurotoxicity in delirium.

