6. STUDY PROCEDURES

6.1. STUDY FLOW CHART

Forty-six surgical patients will be randomized 1:1 to a prospective interventional parallel arm double-blinded placebo-controlled trial. All patients will undergo baseline cognitive screening, 3D-CAM assessment, and DRS-R-98 scoring at the enrolment visit. The intervention arm will receive five doses of oral fluvoxamine capsules, 100mg the night before surgery, 100mg twice daily on the day of surgery and on POD 1; pharmacokinetic modeling predicts high sigma-1 receptor binding at POD 1-2, coinciding with anticipated peak delirium incidence.³⁰ A placebo capsule will be administered at the same schedule for those in the control arm.

Outcome measures include: (1) Feasibility: Incidence and reasons for screen failures and withdrawals, (2) Safety/feasibility: incidence/severity/relatedness of adverse events, number/reasons of missed study drug administrations, (3) Feasibility: Incidence and reasons for missed outcome measurements, (4) Feasibility: Delirium incidence/severity (3D-CAM-S) at enrollment, POD 1-4 (both AM and PM), (5) Feasibility: IL-8 and NfL on POD 1 AM and POD 2 AM, and (6) Feasibility: awake EEG SWA on POD 1 AM and POD 2 AM.

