6.2.2 ADVERSE EVENTS/SERIOUS ADVERSE EVENTS

Rates of nausea, diarrhea, headache, and insomnia will be evaluated from evening before surgery through POD 3 for individuals in both the intervention and control arms. These rates will be tabulated for all events, with consideration of severity and potential relatedness to fluvoxamine or drug-drug interactions.

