6.8. END OF STUDY TREATMENT/WITHDRAWAL PROCEDURE

The study will end 30 days after surgery.

If at the 30-day cognitive screening, there is measured cognitive decline, this will be reported to the PI and if required discussed with the treating medical team, the patient and/or their GP for ongoing care.

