7. OUTCOMES

7.1. DEFINITION OF OUTCOMES

Delirium severity will be defined using the Delirium Rating Scale Revised-98 (DRS-R-98)

Delirium incidence will be defined using the 3D-CAM and administered as described.^{32,33}

Acquisition of EEG recordings and quantification of awake EEG SWA (EEG power 0.5-6 Hz) will proceed as published previously by our group.¹⁴

Blood will be processed with quantitation of IL-8 and NfL as we have previously described.³⁴ At Royal Prince Alfred Hospital patients will have CRP, WCC and troponin sent as SOC.

Rates for enrollment will be calculated with denominators of total eligible and total approached for consent. The rate of screen failures will provide information on the surgical volume and coordinator staff required. A high number of study refusals due to concerns of study drug or type/number of outcome assessments will provide valuable information on revising the study design and/or administration of study procedures for a future investigation. Enrollment rates of <25% based on total approached for consent will warrant revision of study design or additional sites in a future larger scale trial.

Rates of adherence will be computed based on the intake of each dose of study drug, with adherence defined as at least 80% of doses taken (4 of 5 total doses). Reasons for not taking study medication will be classified into the following categories: 1) forgetfulness, 2) misunderstanding, 3) interference with medical care, 4) possible side effects, 5) fear/stress, 6) lack of time.

Rates of data acquisition for CAM assessments, EEG recordings, and IL-8 sampling will be compiled at each time point. Less than 90% collection rate for interpretable outcome measures will constitute a “no go” signal, warranting revision of schedule of activities or pipeline for processing biomarkers.

Adverse events (AE) of nausea, diarrhea, headache, and insomnia will be evaluated from evening before surgery through POD 3. A high rate of AEs directly related to the study drug (>30%) combined with an overall adherence rate of <80% will constitute a “no go” signal for a larger clinical trial.

Postoperative pain scores will be determined using the visual analogue scale (VAS)

Patients at RPAH, will have a thromboelastograph sent prior to start of surgery to monitor platelet function.

Change in cognition and disability at 30 days postoperatively

Blood loss

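### Active adverse-event enquiry stops at POD3 or POD4, while drug is still present and follow-up runs to POD30, so the count of serious events by arm may be incomplete

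*Protocol*

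**What the plan says.** **Persistence of the drug.** Section 1.2 of the protocol says: "The serum half-life is approximately 21 hours". It adds that "the drug becomes concentrated in the brain²⁶ with a brain half-life twice that for plasma", and counts this as an advantage because "slow redistribution from the brain may be ideal for reducing neuroinflammation and delirium severity even after discontinuation".

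**Last dose.** After a dose on the night before surgery, section 6.1 schedules "100mg twice daily on the day of surgery and on POD 1". The final dose is therefore the evening dose on POD1.

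**Safety enquiry.** The protocol gives more than one window:
- The visit table in section 6.2.1 ticks the adverse and serious adverse event row at Visits 3, 4 and 5 (POD1 to POD3). Visit 6 (POD4) and Visit 7 (POD30) are blank.
- Section 6.2.2 says the rates of four named symptoms "will be evaluated from evening before surgery through POD 3 for individuals in both the intervention and control arms". Section 7.1 repeats the POD3 end.
- Section 12.1 places adverse-event assessments at Visits 2 to 6, that is, up to POD4.

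**End of follow-up.** Section 6.8 says: "The study will end 30 days after surgery". In the Visit 7 column only the cognitive screen is ticked. Its footnote lists TICS-M, verbal fluency, WHODAS and GDS15.

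**Serious events.** Section 12.1 counts hospitalisation and death as serious. Section 12.2 requires every serious event to go to the sponsor and the ethics committee at once. It sets no end date and describes no means of finding events after the in-hospital visits.

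**The concern.** Safety and tolerability form a secondary objective (section 3.2), and safety is a secondary endpoint (section 4.4). The protocol relies on the drug lasting in the brain after dosing stops as a reason to expect benefit, but closes active safety enquiry while, on the same figures, much of that drug is still there. It then contacts participants at POD30 without a scheduled question about serious events.

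Eligibility in section 5.1 needs only a two-day stay, so many participants may be home by POD3 or POD4. Readmission is a serious event by the protocol's own definition and can occur only after discharge. Section 1.1 names readmission and mortality among the consequences associated with perioperative delirium, and section 6.3 names bleeding and hyponatraemia among possible drug risks. Such events are foreseeable in this population, yet after POD4 the schedule leaves their discovery to chance. At stake is the completeness of the serious-event count by arm, which those planning the larger trial will read as the safety record of this pilot.

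**Working it through.** There is no plan figure to reproduce: the half-life is an input. The check asks how much drug remains when enquiry stops, and how much of the uncovered period residual drug can explain.

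**Inputs**
- Serum half-life: 21 h (section 1.2).
- Brain half-life: 2 × 21 = 42 h (section 1.2).
- Last dose: evening of POD1 (section 6.1). No clock time is given; 20:00 is assumed, with a range of 16:00 to 22:00.
- End of enquiry: POD3 (visit table, 6.2.2, 7.1) or POD4 (12.1). 20:00 is assumed, with a range of 06:00 to 20:00.

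**Fraction left.** With first-order decay, the fraction of the level just after the last dose is 0.5^(t / half-life).

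| Enquiry ends | t | Serum | Brain |
|---|---|---|---|
| POD3, 20:00 | 48 h | 0.5^(48/21) = 20.5% | 0.5^(48/42) = 45.3% |
| POD4, 20:00 | 72 h | 0.5^(72/21) = 9.3% | 0.5^(72/42) = 30.5% |

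Over the assumed clock times the ranges are:
- POD3: serum 18–35%, brain 42–59%.
- POD4: serum 8–16%, brain 29–40%.

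**How far residual drug carries the argument.** Five half-lives is taken as a conventional marker of near-complete elimination; the protocol sets no such rule.
- Serum: 5 × 21 = 105 h = 4.4 days after the last dose, early on POD6.
- Brain: 5 × 42 = 210 h = 8.75 days after the last dose, during POD10.
- At POD30, 29 × 24 = 696 h after the last dose, the brain fraction is 0.5^(696/42), about 0.001%.

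**Splitting the uncovered period**
- From POD3 to POD30 is 27 days; from POD4 it is 26.
- Residual drug accounts for the part up to POD6 (3 days after POD3, or 2 after POD4) on the serum figure, or up to POD10 (7 or 6 days) on the brain figure.
- The remaining 20 days from POD10 to POD30 are not a half-life matter. They are days on which the trial still follows participants but schedules no enquiry about serious events.

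**The case against.** Several points on the other side stand and limit the claim.

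- **A reader might infer that late harms cannot be counted or would never reach the DSMB.** The protocol does not support that. Section 12.2 has no end date, so a serious event that comes to the site's notice before day 30 must be reported. Blood loss is an endpoint and goes to the DSMB after every 10 patients randomised (section 6.3). The accurate description is that late serious events are not actively sought.
- **A reader might infer that the half-lives justify enquiry to POD30.** They do not. They support roughly POD6 to POD10, and nothing in the protocol ties safety follow-up to a number of half-lives. Residual drug shows exposure; it does not show that harm is expected.
- **A reader might infer that efficacy is followed to POD30 while safety is dropped.** Delirium, sedation and pain scores end at POD4, and EEG and IL-8/NfL by POD2. Only the cognitive screen reaches POD30. It also covers disability and depression, and section 6.8 sends measured cognitive decline to the principal investigator. Some late harm would thus surface as an outcome, though not as an adverse event.
- **The go/no-go decision would not change.** The rule in section 7.1 needs more than 30% drug-related adverse events together with adherence below 80%, and it follows directly on the POD3 symptom window.
- **The numbers are small.** With 46/2 = 23 patients per arm, zero events still leaves a one-sided 95% upper limit of 1 − 0.05^(1/23), about 12%. No useful comparison between arms is possible. That argues against a test, not against a complete count.
- **The case report form is an attachment that is not shown**, and its POD30 page might carry a safety question. The visit table should still state the enquiry, since that is where the protocol fixes what is asked and when.

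**Conclusion.** The point holds as a modest, cheaply corrected gap in ascertainment. Active enquiry ends at POD3 or, at the latest, POD4. On the protocol's own half-lives, drug is still present at either date: about 20% (serum) and 45% (brain) at 48 hours, 9% and 30% at 72 hours. Between 26 and 27 of the 30 postoperative days have no scheduled safety enquiry. Residual drug is the reason for concern up to about POD6 to POD10; after that the reason is simply that the trial still follows participants without asking. The consequence is that the serious-event count by arm may be incomplete. How incomplete cannot be derived from the document.

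The figures assume single-compartment first-order decay and the clock times given, and are relative to the level just after the last dose. Varying the clock times does not alter the conclusion. The primary endpoint (enrolment) and the go/no-go rule are unaffected.

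Separately, the visit table and sections 6.2.2 and 7.1 conflict with section 12.1 on when adverse-event assessment ends. Those passages must be reconciled, but doing so would not close the gap to POD30.

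**What to change.** - In the visit table of section 6.2.1, tick the adverse and serious adverse event row at Visit 7 (POD30).
- At that contact, ask about serious events, readmission and bleeding since the last adverse-event check.
- State that serious adverse events will be reported by arm to POD30, descriptively and without a test.
- Leave the POD3 window for the common symptoms, and the go/no-go rule built on it, as they are.
- Reconcile the adverse-event schedule between the visit table, sections 6.2.2 and 7.1, and section 12.1.

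The cost is one tick and a few questions at a contact that already takes place; no new visit is needed. The drawback is imperfect recall over 30 days, especially of minor events, which is why the enquiry should be limited to serious ones. It would pick up hyponatraemia only where that led to a serious event or readmission.

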2. HYPOTHESIS

We hypothesize that >25% of approached patients will be enrolled in the study. We also hypothesize that >80% enrolled patients will be adherent to oral fluvoxamine or placebo doses, and >90% of interpretable outcome measures will be obtained.

3. STUDY OBJECTIVES

3.1. PRIMARY OBJECTIVES:

Assessing the enrolment rate of approached patients in this pilot study to determine the feasibility of a larger trial

3.2. SECONDARY OBJECTIVES

The safety and tolerability of perioperative fluvoxamine.

The incidence of delirium (3D-Confusion Assessment Method (CAM) or CAM ICU)

Severity of delirium (Delirium Rating Scale-Revised-98 (DRS-R-98))

POD1+2 changes in IL-8 and NfL

Rate of successful biomarker collection on POD1+2

EEG SWA on POD1+2

Rate of successful EEG data collection on POD1+2

Postoperative pain score

Postoperative RASS score

Change in cognition and disability at 30 days postoperatively

Blood loss

Thromboelastography differences on the day of surgery prior to incision at RPAH only

Differences in CRP, WCC or troponin at RPAH only

4. STUDY DESIGN

4.1. DESIGN

Double blind randomized controlled trial.

4.2. EXPECTED PARTICIPANT NUMBERS

46 participants at Royal Prince Alfred Hospital, Sydney, Australia and University of Washington, St Louis, USA

4.3. DURATION OF THE STUDY

1 year

4.4. ENDPOINTS

PRIMARY ENDPOINTS

Trial enrolment rate

SECONDARY ENDPOINTS

The safety of perioperative flvoxamine
--

The incidence of delirium on POD1–4 (3D-Confusion Assessment Method (CAM) or CAM-ICU)

Severity of delirium on POD 1–4 (Delirium Rating Scale Revised-98 DRS-R-98))
--

Rate of protocol adherence

Rate of completed 3D-CAM assessments

Peak delirum severity on POD1–4

Collection rate of biomarkers (IL-8 + NfL) and EEG recording on POD1+2
--

EEG slow wave activity (0.5–6Hz) on POD1+2
--

POD1+2 changes in IL-8 and NfL

RASS score on POD1–4

Postoperative pain score
Change in cognition and disability at 30 days postoperatively
Blood loss
Thromboelastography on the day of surgery prior to incision at RPAH only
CRP, WCC and troponin

